- 5. An individual for whom the caregiver decides not to permit participation in the study will continue to work with the physician on the ASD treatment plan goals for the minor patient.

Compensation

A subject or his or her caregiver(s) will not be offered money or any other form of compensation to participate in the clinical study; however, there will also not be any charge for the cost of the study treatments with the Erchonia® HLS laser device or for the cost of any other directly-related evaluations or measurements that occur as part of the subject's participation in this study.

Subject Sample Size

There will be 40 qualified subjects enrolled in this clinical study:

- 20 subjects in the test group
- 20 subjects in the control (placebo) group

Rationale and Justification for Sample Size

This study is powered to compare one active arm with placebo. Sample size calculation is based on the primary efficacy measure of the mean change from study baseline to endpoint (end of the 4-week treatment period) in the Aberrant Behavior Checklist (ABC) Irritability Subscale score adjusted for the baseline ABC Irritability Subscale score.

Based on detecting a mean difference of -8.5 points between test and placebo groups in the change in ABC Irritability Subscale score adjusted for the baseline ABC Irritability Subscale score being considered clinically relevant with a SD of 8.9, a two-sided test with 80% power and a 5% level of significance, the number of subjects needed per treatment group is 18.

From here, it is anticipated that about one-tenth of subjects overall may withdraw or be terminated from the study prior to completion for various reasons. Therefore, the following formula is used to determine the final needed starting sample size for each procedure arm:

Final sample size = sample size X 1/(1-d); where d = # expected dropouts/# subjects enrolled.

Final sample size = $18 \times 1/(1-0.11)$; where d = 2/19

Final sample size = 18 X 1/0.89 = 18 X 1.124 = 20 subjects per treatment group.

Therefore, a minimum starting sample size of 20 subjects in each treatment group (40 subjects in total) is needed to insure that a sufficient number remains at study endpoint (18 evaluable subjects per treatment group) for any significant differences found between treatment groups to be considered statistically valid and representative of the general population being sampled.

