For the continuous primary efficacy measure of ABC Irritability Subscale score, change scores will be evaluated by analysis of covariance (ANCOVA). The ANCOVA models for LOCF data sets will include the baseline measure as a covariate and treatment (active of placebo) as main effects.

Secondary Measures Analysis

- ➤ For the continuous secondary efficacy measures of the other 4 ABC Subscale scores, and the Global Score, change scores will be evaluated by analysis of covariance (ANCOVA). The ANCOVA models for LOCF data sets will include the baseline measure as a covariate and treatment (active of placebo) as main effects. A two-way significance level of 5% will be considered statistically significant.
- ➤ The categorical measures of the CGI will be analyzed within the framework of the generalized Cochran-Mantel Haenszel (CMH) procedure.
- Responder rate will be evaluated using Fisher's exact test to compare the proportion of responder rates between the test and control groups.

P-values will be 2-tailed tests of significance rounded to 3 decimal places. All analyses will be performed at the 5% significance level.

CAREGIVER SATISFACTION

Caregiver satisfaction ratings will be descriptively presented through the number and percentage of responses per response category. Fischer's Exact Test will be employed to determine the significance of the difference in categorical responses between treatment groups.

BLINDING EFFICACY EVALUATION

Blinding efficacy evaluation will be conducted through analysis of findings from the Caregiver and the Assessment Investigator Perceived Subject Group Allocation and Rationale responses, recorded at completion of the procedure administration phase (study endpoint).

Statistical evaluation of blinding efficacy will be performed as follows:

- (i) The percentage of caregivers who correctly perceived the subject's procedure group assignment and the percentage of caregivers who did not correctly perceive the subject's procedure group assignment will be calculated.
- (ii) The percentage of times the assessment investigators correctly perceived subjects' procedure group assignment and the percentage of times the assessment investigators did not correctly perceive subjects' procedure group assignment will be calculated.

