- (iii) The **Fischer's Exact categorical analysis technique** for comparison of proportion of successes (accurate procedure group assignment determination) and failures (inaccurate procedure group assignment determination) between subject

- groups will be performed for each of the caregiver and assessment investigator determinations.
- (iv) **Qualitative analysis confirmation:** Evaluation of the comments provided by the caregiver and assessment investigators in the rationale section to explain the guess at group assignment will be evaluated and interpreted as follows to either support or negate the numerical findings:
 - Positive blinding efficacy will be supported through qualitative assessment of comments provided to support perceived group assignment that pertain to the determination being made based on treatment efficacy or lack thereof; e.g.: 'My child has been calmer and communicating better lately, so I think he got the real treatment' or 'I haven't noticed any change in my child's behavior at all, so I believe he got the fake treatment.'
 - Blinding will be determined to have failed if comments provided to support perceived group assignment pertain to factors such as sensation/visual clues, such as 'I saw/didn't see a light go on the laser', or other factors that pertain to blinding having been compromised such as 'I overheard the doctor saying my child was/wasn't getting the real treatment.'

SAFETY ANALYSES

Safety analyses will be completed on all subjects who were randomized to treatment group and received at least the first study treatment administration with the Erchonia® HLS Laser device.

Safety will be assessed by evaluating and comparing frequency and incidence of observed and/or reported adverse events between test and placebo treatment groups. A chi-square test with a continuity correction will be performed to compare the percentage of subjects who had adverse events and/or reactions between the test and placebo group subjects.

SAFETY AND CONFIDENTIALITY ISSUES

ADVERSE EVENTS

At any time throughout the study, any adverse event reported by a subject and/or subject's caregiver and/or observed by the study investigator will be recorded on the case report form and subsequently evaluated by the Principal Investigator for its relation to the study treatment and whether or not any corrective action need be taken. All applicable adverse events will be reported to the IRB and EC, if applicable.

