Formal evaluation of the occurrence of any adverse events will take place at the end of each study treatment administration and each evaluation visit. In addition, subjects/caregivers will be instructed to contact the investigator at any other time that he or she believes a potential adverse event has occurred throughout the subject's participation in the clinical study.

The investigator will record the observation or report of any adverse event and assign the relationship to the study treatment on the appropriate case report form in the subject's file and will report the occurrence to the governing IRB, if and as appropriate, within 5 days of the reported occurrence, or within 24 hours in the occurrence of a serious adverse event including death.

The only known potential adverse event associated with the use of laser devices is that long-term exposure to laser light could cause damage to eyesight. As a precaution, during all laser treatment administrations with the Erchonia® HLS at the test site, both the subject and the administration investigator will wear safety glasses that filter out the laser light spectrum. The administration investigator will wear KenTek Corporation KenTek C22-KMT-6101 light blue safety glasses and the subject will wear KenTek Corporation KGOG-6101 light blue Medium Goggles safety goggles. Additional information on this safety eyewear is contained above on pages 6-8 under the section titled: DEVICE SAFETY: RISK AND PREVENTION OF EYE INJURY.

There are no other known potential adverse events from application of the study lasers. There have been no observed or reported adverse events or reactions to the application of the family of Erchonia® laser devices in several other studies using these laser devices. However, potential adverse events that may occur include, but are not necessarily limited to: skin irritation, skin discoloring, skin rash, skin indentations and infection. There may also be unknown or unanticipated risks to using the laser devices with this study treatment.

MONITORING OF THE CLINICAL STUDY

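### Adverse events are compared by a continuity-corrected chi-square, which in sparse tables is less sensitive than the Fisher's exact test used elsewhere in the plan and cannot be computed if no child has an event

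*Combined protocol and SAP*

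**What the plan says.** The Safety Analyses section of the Statistical Analysis Plan sets the test: "A chi-square test with a continuity correction will be performed to compare the percentage of subjects who had adverse events". The analysis set is defined there too: "Safety analyses will be completed on all subjects who were randomized to treatment group and received at least the first study treatment administration". The section gives no rule for small or empty cells.

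Subject Sample Size plans "20 subjects in the test group" and "20 subjects in the control (placebo) group". The Statistical Analysis section adds "P-values will be 2-tailed tests of significance rounded to 3 decimal places" and "All analyses will be performed at the 5% significance level".

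On what to expect, the summaries of earlier work report no adverse event in the 11-subject feasibility study and none in the 40-subject randomized study. The Adverse Events section says of the wider device family: "There have been no observed or reported adverse events or reactions to the application of the family of Erchonia® laser devices". That sentence refers to several other studies. The text then lists skin events and infection as possible. No expected event rate is stated.

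The plan's other between-group comparisons of proportions or categories outside the CGI use Fisher's exact test: responder rate, caregiver satisfaction, and correct guesses of allocation in the blinding evaluation.

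**The concern.** The chi-square relies on a large-sample approximation, usually trusted when expected counts reach about 5 per cell. With 20 per arm, each arm's expected number of children with an event is half the total, so at least 10 of the 40 children would need an event. The device's history points to far fewer. If there are none, the statistic is 0/0 and the plan names no alternative, so the analyst would have to choose one once the data are known.

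This is the plan's only formal between-group safety test, in children aged 5 to 12. Missing a real excess is the costlier error here, and a conservative test leans that way. The plan gives no reason for using an approximation on the comparison that its own history suggests will be the sparsest.

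**Working it through.** **Table size.** The plan's sample size starts from "Based on detecting a mean difference of -8.5 points between test and placebo groups", with SD 8.9, two-sided 5% and 80% power. n = 2 × (1.960 + 0.842)² × 8.9² / 8.5² = 17.2, so 18 evaluable per arm, as stated. Allowing for dropout, 18 / 0.89 = 20.2, which the plan takes as 20. The 18 is the number needed for efficacy at the endpoint. The safety set keeps children who drop out after a first treatment, so 20 v 20 is the relevant table. It becomes unequal if a randomized child is never treated.

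**Formulas.** For a table with rows (a, b) and (c, d) and total N, the corrected chi-square is N(|ad − bc| − N/2)² / (product of the four margins), referred to 1 degree of freedom. Two-sided Fisher sums the hypergeometric probabilities of all tables no more likely than the one observed.

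**5/20 v 0/20.**
- Corrected chi-square: 40 × (100 − 20)² / (20 × 20 × 5 × 35) = 256,000 / 70,000 = 3.657, p = 0.056. The smallest expected count is 2.5.
- Fisher: 2 × C(20,5) / C(40,5) = 2 × 15,504 / 658,008 = 0.047.

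**11/20 v 4/20.**
- Corrected chi-square: 40 × (140 − 20)² / (20 × 20 × 15 × 25) = 576,000 / 150,000 = 3.840, p = 0.05004, reported as 0.050 to three decimals.
- Fisher: 0.048.

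**4/19 v 0/20.**
- Corrected chi-square: 39 × (80 − 19.5)² / (19 × 20 × 4 × 35) = 142,750 / 53,200 = 2.683, p = 0.101.
- Fisher: C(19,4) / C(39,4) = 3,876 / 82,251 = 0.047. The mirror table (0/19 v 4/20) has probability 4,845 / 82,251 = 0.059. It is more likely than the observed table, so it is not counted.

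**0/20 v 0/20.** The event margin is zero, so the chi-square is 0/0. Fisher gives p = 1.

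**All tables.** Enumerating every table at 20 v 20, the tests disagree at 5% for 5 v 0, 11 v 4 and their complements (20 v 15 and 16 v 9), in either direction. That is 4 of the 21 × 20 / 2 = 210 pairs of unequal counts. On either side of 5 v 0 they agree: 4 v 0 gives Fisher 0.106 and chi-square 0.114, and 6 v 0 gives 0.020 and 0.027. At 19 v 20 there are more splits, such as 6/19 v 1/20 (0.044 and 0.081) and 8/19 v 2/20 (0.031 and 0.054). In all the arm sizes from 18 to 20 that were enumerated, no table was significant by the chi-square and not by Fisher.

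**Power at 20 per arm, assumed true rates 25% v 0%.** Fisher rejects when 5 or more treated children have an event: P = 0.585. The corrected chi-square needs 6 or more: P = 0.383. The gap, 0.202, is the probability of exactly 5. At an assumed 30% v 0%, power is 76% and 58%.

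**How sparse the table may be.** The plan gives no rate, so these common rates are assumptions.

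| Assumed rate | P(no child has an event) | P(9 or fewer in total) |
|---|---|---|
| 1% | 67% | >99.9% |
| 5% | 13% | >99.9% |
| 10% | 1.5% | 99.5% |
| 20% | <0.1% | 73% |

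The second column is (1 − rate)^40; the third is the binomial probability for 40 children.

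**The case against.** The strongest reply is that the choice of test would rarely matter. If events really are rare, at 20 v 20 neither test can reach 5% with 4 or fewer affected children in total. The probability of 4 or fewer is above 99.9%, 99.9% and 95% at assumed common rates of 1%, 2% and 5%. The tests separate only if there is a large true excess, and even at 25% v 0% the deciding table occurs about 20% of the time. At 0 v 0, Fisher's p = 1 adds nothing to the two zeros. The plan already commits to comparing the frequency and incidence of events by group, the Principal Investigator evaluates each event, and no decision rule uses this p-value. All of that stands, and it limits the weight of the point.

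The wide gap at 4/19 v 0/20 also owes something to how two-sided Fisher is defined: the opposite tail drops out. In the other direction, 0/19 v 4/20, Fisher gives 0.059 + 0.047 = 0.106.

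A reader might infer three stronger things that the documents do not support.
- **That the planned test is invalid.** The expected count of 5 is a rule of thumb, and the correction errs on the safe side for false positives: at an assumed common rate of 5% its true size is 0.0003, against 0.0019 for Fisher.
- **That the sponsor forecasts almost no events.** The history suggests it, but no rate is stated, possible events are listed, and any adverse event over the 8 weeks is recorded.
- **That 18 per arm is a safety scenario.** That number is the efficacy requirement.

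**Conclusion.** The point holds as a minor one. The named test is conservative in the tables that this trial is likely to produce, cannot be computed if nobody has an event, and departs without explanation from the exact test used for responder rate, satisfaction and blinding. At equal arms its effect on a 5% conclusion is confined to a few borderline tables, always towards missing a difference that Fisher would call significant. The loss of power (59% to 38%, or 76% to 58%) rests on assumed excesses of 25 or 30 percentage points over a zero placebo rate. For rare events neither test is useful at this size, so intervals matter more than the p-value. Study success depends on the primary endpoint alone and is untouched.

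**What to change.** In Safety Analyses, replace the continuity-corrected chi-square with a two-sided Fisher's exact test. Add that each arm's proportion of children with an event, and the between-arm difference, will be reported with exact 95% confidence intervals, and name the interval methods. A zero count then still informs: for 0/20 the exact two-sided upper limit is 1 − 0.025^(1/20) = 16.8%. An exact interval for the difference need not agree with Fisher's p-value in borderline tables, so say which one leads the interpretation. The cost is a sentence or two in the plan, settled before unblinding. No extra data or subjects are needed, and in the tables enumerated Fisher was never the less sensitive test at 5%.

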Western Institutional Review Board® (WIRB®) [name] [contact]

www.wirb.com

PURPOSE OF STUDY

The purpose of this clinical study is to demonstrate the efficacy of the Erchonia® HLS laser device, manufactured by Erchonia Corporation (the Sponsor), for the treatment of symptoms of irritability associated with autistic disorder in children aged five to twelve years, inclusive.

The Sponsor intends to submit the data and analysis from this study via a de novo application to obtain FDA clearance to market the laser device for the intended indication.

LABELING

Once cleared for market in the U.S., the Erchonia® HLS laser device will be labeled as prescription device, per 21 CFR § 801.109.

INDICATION FOR USE

The results of this clinical study will be used to support the following indication for use: "The Erchonia® HLS laser device is indicated to improve the symptoms of irritability associated with autistic disorder in children aged five to twelve years, inclusive."

REGULATORY HISTORY

This clinical study protocol design is a cumulative result of the following regulatory history.

- 1. FDA Pre-IDE#I120613 review of the following protocol: The Erchonia® HLS Laser Device: A double-blind, placebo-controlled randomized evaluation of the effect of the Erchonia® HLS laser device on children and adolescents with autistic disorder clinical study protocol; Version 1.1, June 26, 2012; Sponsor: Erchonia Corporation.
 - (i) Submitted to the FDA by the Sponsor on 7/15/12
 - (ii) FDA's written review received by the Sponsor on 1/17/13
 - (iii) Sponsor response submitted to FDA on 2/5/13 along with the requested Supplement protocol (V2.0 1/31/13) reviewed as Q130138
 - (iv) FDA's written review for Q130138 received by the Sponsor on 4.23.13
- 2. DEN180046: De Novo submission to FDA made by the Sponsor on 8/28/18 supported by the results of the clinical study based on the outcome of the FDA's written review of Q130138.

- (i) Two rounds of FDA Interactive Review questions ensued with responses submitted by the Sponsor within the requested timeframe in both instances
- (ii) FDA's written Request for Additional Information (RAI) received by the Sponsor on 1/23/19
- (iii) Sponsor's response to the RAI submitted on 2/26/19
- (iv) FDA Denial of De Novo request received by the Sponsor on 5/22/19

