CONCLUSION: The Erchonia® HLS Laser is an effective tool for improving irritability and the presentation of other symptoms and behaviors associated with autistic disorder in children and adolescents, with positive changes maintained and augmented over time, including a six-month follow-up period during which time no procedure administration occurred.

STUDY RATIONALE

Considering the positive outcomes of the prior feasibility and clinical studies, it is determined that application of the Erchonia® HLS may provide a simple, non-invasive, safe, effective and side-effect free alternative therapy to reduce the severity of irritability symptoms and behaviors of autistic disorder in children. The currently proposed full-scale controlled pivotal trial is intended to demonstrate this to a statistically significant and clinically meaningful extent.

STUDY DESIGN

This clinical study is a double-blind, placebo-controlled randomized parallel group design.

TREATMENT GROUPS

Each subject is randomized to the test treatment group or to the placebo treatment group, as follows:

- ➤ Test Group: Subjects randomized to the test group will receive the study treatments with the active (true) Erchonia® HLS device.
- ➤ Placebo Group: Subjects randomized to the placebo group will receive the study treatments with the 'fake' (placebo) Erchonia® HLS device.

DOUBLE BLIND DESIGN

This clinical study will be a double-blind design, such that neither the subject nor the investigator will be aware of whether a subject has been assigned to the test group or to the control group until after the study is complete.

Maintenance of study double-blind throughout the study duration will be achieved as follows:

- 1) Each subject will be randomly assigned to Treatment Group A or to Treatment Group B. Subjects assigned to Treatment Group A will be treated with the Erchonia® HLS A and subjects assigned to Treatment Group B will be treated with Erchonia® HLS B. Only the study Sponsor will know which label ('A' or 'B') corresponds to the actual (test) HLS device and which label corresponds to the 'fake' device until the final study data analysis is complete. The Sponsor will ensure that this information is stored and maintained confidentially at the Sponsor's work site. This knowledge will not be shared with the investigators, the subjects, or the study Monitor until the final data analysis is complete.

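### The rationale's safety wording goes further than the planned adverse-event analysis, whose only inference is a test that can rule out very little harm at 20 per arm

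*Combined protocol and SAP*

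**What the plan says.** The Study Rationale states that the device "may provide a simple, non-invasive, safe, effective and side-effect free alternative therapy" for irritability in autistic disorder. The next sentence says the pivotal trial "is intended to demonstrate this to a statistically significant and clinically meaningful extent".

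The opening Purpose of Study section is narrower: "The purpose of this clinical study is to demonstrate the efficacy of the Erchonia® HLS laser device". The sample size, the aim and success rule of the Statistical Analysis Plan, and its hypotheses likewise concern efficacy on the ABC Irritability Subscale.

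The Safety Analyses section covers randomised children who "received at least the first study treatment administration with the Erchonia® HLS Laser device". It plans a descriptive step, "Safety will be assessed by evaluating and comparing frequency and incidence of observed and/or reported adverse events between test and placebo treatment groups", and one test: "A chi-square test with a continuity correction will be performed to compare the percentage of subjects who had adverse events and/or reactions". The general rule under Statistical Analysis makes tests two-sided at 5%. No interval, margin, acceptable excess or safety power is given anywhere.

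**The concern.** A test of no difference can point to harm, but failing to reject does not show that harm is absent. If the rationale is taken at its word, the only formal support that the plan could offer for its safety wording is a non-significant p-value or an absence of events. At this sample size, a non-significant p-value is the likely result even if the device causes a sizeable excess of adverse events in children aged 5 to 12. The report would then carry no figure for how much harm the data leave open, and the results are meant to support a marketing application.

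**Working it through.** **Inputs from the documents.** Planned enrolment is "20 subjects in the test group" and the same number on placebo. The safety set is everyone randomised and treated at least once, so at most 20 per arm. The test is chi-square with continuity correction, two-sided at 5%.

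**Assumptions.** The documents give no expected adverse-event rate and no excess that would matter. I take a 20-point excess and vary the placebo rate from 0% to 30%. A placebo rate of 0% matches the earlier controlled study, which reported no adverse events.

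**The plan's own figure.** The efficacy sample size reproduces: n = 2(1.96 + 0.84)² × (8.9/8.5)² = 17.2, rounded up to 18 per arm; then 18/0.89 = 20.2, given as 20. Safety plays no part in it.

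**Significance boundary.** With a and b affected out of 20 per arm, N = 40 and m = a + b, the corrected statistic is

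X² = 40 × (|20a − 20b| − 20)² / (20 × 20 × m × (40 − m)).

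- 5 v 0: 40 × 80² / (400 × 5 × 35) = 3.66, p = 0.056.
- 6 v 0: 40 × 100² / (400 × 6 × 34) = 4.90, p = 0.027.
- 0 v 0: m = 0, so the denominator is zero and the statistic is undefined.

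With no placebo events, at least 6 of 20 active children must therefore be affected before p falls below 0.05.

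**Chance of missing a 20-point excess.** This comes from exact enumeration of two binomials at 20 per arm, with 0 v 0 counted as not significant. At 0% v 20% it reduces to P(X ≤ 5) for X ~ Bin(20, 0.20), which is 0.804.

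| Placebo v active | Planned test | Fisher | Uncorrected Pearson |
|---|---|---|---|
| 0% v 20% | 80% | 63% | 41% |
| 5% v 25% | 77% | 70% | 56% |
| 10% v 30% | 78% | 76% | 64% |
| 20% v 40% | 82% | 81% | 71% |
| 30% v 50% | 86% | 84% | 76% |

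With the planned test, a 30-point excess (10% v 40%) is still missed 52% of the time. Power of 80% needs an excess of about 37 points at a placebo rate of 0%, or 44 points at 10%.

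**What an interval would show.**

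- 5/20 v 0/20: the Wilson limits are 11.2% to 46.9% and 0% to 16.1%. The Newcombe lower limit is 0.25 − √[(0.25 − 0.112)² + 0.161²] = 0.038 and the upper limit is 0.469, so the difference is +4 to +47 points. The interval excludes zero while the planned test says not significant.
- 0/20 active: the exact one-sided 95% upper limit is 1 − 0.05^(1/20) = 13.9%.
- 0/20 v 0/20: the Newcombe 95% interval for the difference is −16 to +16 points.

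**The case against.** The strongest reply is that no confirmatory safety objective exists. Purpose, indication, sample size, hypotheses and success rule are all about efficacy. The rationale is hedged with *may*, and the *this* that the trial is to demonstrate could refer mainly to symptom reduction. That stands. A reader might infer that the trial has a formal safety aim which it then fails to test. The documents do not support that; they support only that one rationale passage promises more than the safety analysis can give.

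A reader might also infer that the sponsor will present p>0.05 as proof of safety. Nothing in the documents says so, and the Adverse Events section itself warns of possible unknown risks. The plan is silent on how a non-significant result will be read, and that silence is what needs filling.

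Adverse-event frequency and incidence by arm are already planned, so an interval could be computed from the counts. That also stands. The gap is that the plan commits to a p-value and not to an interval.

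The size of the problem depends partly on the test. At 0% v 20% the miss rate falls from 80% to 63% with Fisher and 41% with uncorrected Pearson, so the continuity correction accounts for much of the figure there. At placebo rates of 10% or more, all three tests miss most 20-point excesses. Weak power for adverse events is usual in a trial of this size, which is a reason to estimate and not to rely on a test.

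Finally, one might pool earlier event-free exposures to tighten the upper limit. Those studies included participants well above 12 years (up to 17 in the controlled study), and it is not stated that the controlled study's event-free report covers its cross-over phase. I do not pool them.

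**Conclusion.** The point holds as a mismatch between the rationale's wording and the safety analysis. It is not a flaw in the primary analysis: the efficacy conclusion, sample size and success rule are unaffected.

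At 20 per arm the planned test misses a true 20-point excess about 77% to 86% of the time over assumed placebo rates of 0% to 30%. It can call a result non-significant when an interval excludes zero (5/20 v 0/20), and it returns nothing in the 0 v 0 case that the sponsor's own history makes plausible. The event rates and the 20-point excess are assumptions. The boundary results (5 v 0, 6 v 0, 0 v 0) and the 13.9% limit need only 20 treated children per arm. Even a perfect record of 0/20 would not justify describing the device as free of side effects.

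**What to change.** In Safety Analyses, make the reported safety result an estimate:

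- the number and percentage of children with any adverse event in each arm;
- an exact one-sided 95% upper limit for the active-arm rate;
- a 95% confidence interval for the difference between arms, for example Newcombe, which remains defined when no events occur.

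Keep any p-value as descriptive, and state that a non-significant result will not be taken as evidence of safety.

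In the Study Rationale, limit what the trial is intended to demonstrate to efficacy, in line with the Purpose of Study, and delete the side-effect-free description. Do not put a rate in its place, because none exists before the data do.

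The cost is a few lines of text and one extra table, with no added children, visits or procedures. The downside is a less favourable safety statement: with no events among 20 active children, the report would say that rates above about 14% are excluded, instead of pointing to an absence of significant difference.
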